#### **4.3 End of post-treatment follow-up (study phase completion)**

End of post-treatment follow-up visit will be completed after discontinuation of study treatment and post-treatment evaluations but prior to collecting survival follow-up.

Patients may provide study phase completion information for one of the following reasons:

- Adverse event
- Lost to follow-up
- Physician decision
- Pregnancy
- Protocol deviation
- Technical problems
- Subject/guardian decision
- Death
- Progressive disease
- Study terminated by the sponsor

#### **4.4 Medical validation of programmed overall lesion response**

In order to be as objective as possible, the RECIST programmed calculated response assessment is very strict regarding measurement methods (i.e. any assessment with more or less sensitive method than the one used to assess the lesion at baseline is considered UNK) and not available evaluations (i.e. if any target or non-target lesion was not evaluated the whole overall lesion response is UNK unless remaining lesions qualified for PD). This contrasts with the slightly more flexible guidance given to local investigators (and to the central reviewers) to use expert judgement in determining response in these types of situations, and therefore as a consequence, discrepancies between the different sources of response assessment often arise. To ensure the quality of response assessments from the local site and/or the central reviewer, the responses may be re-evaluated by clinicians (based on local investigator data recorded in the eCRF or based on central reviewer data entered in the database) at Novartis or external experts. In addition, data review reports will be available to identify assessments for which the investigators’ or central reader’s opinion does not match the programmed calculated response based on RECIST criteria. This may be queried for clarification. However, the investigator or central reader’s response assessment will never be overruled.

If Novartis elect to invalidate an overall lesion response as evaluated by the investigator or central reader upon internal or external review of the data, the calculated overall lesion response at that specific assessment is to be kept in a dataset. This must be clearly documented in the RAP documentation and agreed before database lock. This dataset should be created and stored as part of the ‘raw’ data.

Any discontinuation due to ‘Disease progression’ without documentation of progression by RECIST criteria should be carefully reviewed. Only patients with documented deterioration of symptoms indicative of progression of disease should have this reason for discontinuation of treatment or study evaluation.

#### **4.5 Programming rules**

The following should be used for programming of efficacy results:

##### **4.5.1 Calculation of ‘time to event’ variables**

Time to event = end date - start date + 1 (in days)

When no post-baseline tumor assessments are available, the date of randomization/start of treatment will be used as end date (duration = 1 day) when time is to be censored at last tumor assessment, i.e. time to event variables can never be negative.

##### **4.5.2 Incomplete assessment dates**

All investigation dates (e.g. X-ray, CT scan) must be completed with day, month and year.

If one or more investigation dates are incomplete but other investigation dates are available, this/these incomplete date(s) are not considered for calculation of the assessment date (and assessment date is calculated as outlined in [Section 3.2.8](#)). If all measurement dates have no day recorded, the 1st of the month is used.

If the month is not completed, for any of the investigations, the respective assessment will be considered to be at the date which is exactly between previous and following assessment. If a previous and following assessment is not available, this assessment will not be used for any calculation.

##### **4.5.3 Incomplete dates for last known date patient alive or death**

All dates must be completed with day, month and year. If the day is missing, the 15th of the month will be used for incomplete death dates or dates of last contact.

##### **4.5.4 Non-target lesion response**

If no non-target lesions are identified at baseline (and therefore not followed throughout the study), the non-target lesion response at each assessment will be considered ‘not applicable (NA)’.

##### **4.5.5 Study/project specific programming**

The standard analysis programs need to be adapted for each study/project.

##### **4.5.6 Censoring reason**

In order to summarize the various reasons for censoring, the following categories will be calculated for each time to event variable based on the treatment completion page, the study evaluation completion page and the survival page.

For survival the following censoring reasons are possible:

- Alive
- Lost to follow-up

For PFS and TTP (and therefore duration of responses) the following censoring reasons are possible:

- Ongoing without event
- Lost to follow-up
- Withdrew consent
- Adequate assessment no longer available\*
- Event documented after two or more missing tumor assessments (optional, see [Table 3-2](#))
- Death due to reason other than underlying cancer (*only used for TTP and duration of response*)
- Initiation of new anti-cancer therapy

\*Adequate assessment is defined in [Section 3.2.8](#). This reason is applicable when adequate evaluations are missing for a specified period prior to data cut-off (or prior to any other censoring reason) corresponding to the unavailability of two or more planned tumor assessments prior to the cut-off date. The following clarifications concerning this reason should also be noted:

- This may be when there has been a definite decision to stop evaluation (e.g. reason="Sponsor decision" on study evaluation completion page), when patients are not followed for progression after treatment completion or when only UNK assessments are available just prior to data cut-off).
- The reason "Adequate assessment no longer available" also prevails in situations when another censoring reason (e.g. withdrawal of consent, loss to follow-up or alternative anti-cancer therapy) has occurred more than the specified period following the last adequate assessment.
- This reason will also be used to censor in case of no baseline assessment.

### 14.4 Appendix 4 - Bone Marrow Reserve in Adults

Adapted from R.E. ELLIS: The Distribution of Active Bone Marrow in the Adult, Phy. Med. Biol. 5, 255-258, 1961

#### MARROW DISTRIBUTION OF THE ADULT

SITE		MARROW wt. (g)	FRACTION RED MARROW AGE 40	RED MARROW wt. (g) AGE 40	% TOTAL RED MARROW	
CRANIUM AND MANDIBLE	Head:			136.6		
	Cranium	165.8	0.75	124.3	13.1	13.1
	Mandible	16.4	0.75	12.3		
HUMERI, SCAPULAE, CLAVICLES	Upper Limb Girdle :			86.7		
	2 Humerus, head & neck	26.5	0.75	20.0	8.3	8.3
	2 Scapulae	67.4	0.75	50.5		
	2 Clavicles	21.6	0.75	16.2		
STERNUM AND RIBS	Sternum	39.0	0.6	23.4	2.3	
	Ribs:			82.6		10.2
	1 pair	10.2	All 0.4	4.1	7.9	
	2	12.6		5.0		
	3	16.0		6.4		
	4	18.6		7.4		
	5	23.8		9.5		
	6	23.6		9.4		
	7	25.0		10.0		
	8	24.0		9.6		
	9	21.2		8.5		
	10	16.0		6.4		
	11	11.2		4.5		
12	4.6		1.8			
PELVIC BONES	Sacrum	194.0	0.75	145.6	13.9	
	2 os coxae	310.6	0.75	233.0	22.3	36.2
FEMUR	2 Femoral head and neck	53.0	0.75	40.0		3.8

Appendix 1	CTC grades for laboratory values in Novartis Oncology.....	28

List of tables

Document History – Changes compared to previous version of SAP.....	2
Table 1-1 Study objectives	9
Table 2-1 Last contact date data sources	13
Table 2-1 Patient classification based on protocol deviations and non- protocol deviation criteria	15
Table 3-1 Planned dose intensity.....	18
Table 3-2 Clinically notable ECG values	25

List of figures

Figure 1-1 Study Design	9
-------------------------------	---

List of abbreviations

AE	Adverse event
AESI	Adverse events of special interest
ATC	Anatomical Therapeutic Chemical
BOR	Best overall response
CI	Confidence Interval
CBR	Clinical benefit rate
CR	Complete response
CRF	Case Report Form
CRS	Case retrieval sheet
CSR	Clinical study report
CT	Computed tomography
CTCAE	Common Terminology Criteria for Adverse Events
DAR	Dosage administration Record
DI	Dose Intensity
DOR	Duration of Response
ECG	Electrocardiogram
ECOG	Eastern Cooperative Oncology Group
EORTC QLQ-C30	European Organization for Research and Treatment of Cancer Core 30-item Quality of Life Questionnaire
EOT	End of treatment
ER	Estrogen receptor
FAS	Full analysis set
HER2	Human epidermal growth factor receptor 2
HR	Hazard Ratio
HR	Hormone receptor
MBC	Metastatic breast cancer
MedDRA	Medical Dictionary for Regulatory Activities
NCI	National Cancer Institute
NMQ	Novartis MedDRA queries
ORR	Overall response rate
OS	Overall survival
PD	Progressive disease
PDI	Planned dose intensity
PDS	Programming Datasets Specifications
PFS	Progression-free survival
PR	Partial response
PS	Performance Status
PT	Preferred term
QTcF	QT interval corrected by Fridericia method
RDI	Relative dose intensity
RECIST	Response Evaluation Criteria In Solid Tumors

SAE	Serious adverse event
SAP	Statistical Analysis Plan
SD	Stable disease
SD	Standard deviation
SMQ	Standardized MedDRA queries
SOC	System organ class
TFL	Tables Figures and Listings
TBIL	Total Bilirubin

1 Introduction

This document describes the detailed statistical methodology to be used for the final Clinical Study Report (CSR) for the study CLEE011E2301, a phase III, randomized, double-blind, placebo-controlled study of LEE011 (ribociclib) or placebo in combination with tamoxifen and goserelin or a non-steroidal aromatase inhibitor (NSAI) and goserelin for the treatment of premenopausal women with hormone receptor positive, HER2-negative, advanced breast cancer.

The content of this SAP is based on protocol amendment 7 (clee011e2301-v07--protocol). All decisions regarding final analysis, as defined in the SAP document, have been made prior to database lock and unblinding of the study data.

CSR deliverables (shells for tables, figures, listings) and further programming specifications are described in the Tables, Figures & Listings (TFL) shells and Programming Datasets Specifications (PDS), respectively.

1.1 Study design

This is a phase III randomized, double-blind, placebo-controlled global study comparing the combination of tamoxifen or a NSAI (letrozole or anastrozole) + goserelin + LEE011 to tamoxifen or a NSAI (letrozole or anastrozole) + goserelin + placebo in premenopausal women with HR+, HER2-negative advanced breast cancer.

A total of 672 patients were randomly assigned to one of the below treatment arms in an 1:1 ratio:

[figure not shown]
- a. [Tamoxifen or a NSAI (letrozole or anastrozole)] + goserelin + LEE011
OR,
- b. [Tamoxifen or a NSAI (letrozole or anastrozole)] + goserelin + placebo.

Randomization was stratified by the presence of liver and/or lung metastases (yes versus no), prior chemotherapy for advanced disease (yes versus no), and endocrine combination partner (tamoxifen and goserelin versus NSAI (letrozole or anastrozole) and goserelin).

Following the statistically significant PFS and OS benefit, with protocol amendment 6, study participants were unblinded, with an opportunity for those patients still on study treatment in the placebo combination arm to cross-over to the LEE011 combination arm. Crossover was optional and was conducted only upon documented consent of the study patient.

The study design is summarized in [Figure 1-1](#).

Figure 1-1 Study Design

[figure not shown]
1.2 Objectives

The study objectives and corresponding endpoints as specified in the protocol are provided in [Table 1-1](#). PFS, as assessed by the local radiologists/investigators and using RECIST 1.1 criteria is the primary endpoint. Overall survival is a key secondary endpoint. Both PFS and OS have been tested statistically significant and results have been summarized by previous study reports.

Table 1-1 Study objectives

Objective	Endpoint
Primary	
To determine whether treatment with tamoxifen or a NSAI + goserelin + LEE011 prolongs PFS compared to treatment with tamoxifen or a NSAI + goserelin + placebo in premenopausal women with HR+, HER2-negative advanced breast cancer	PFS per local assessment and RECIST 1.1
Key secondary	
To determine whether treatment with tamoxifen or a NSAI + goserelin + LEE011 prolongs OS compared to treatment with tamoxifen or a NSAI + goserelin + placebo in premenopausal women with HR+, HER2-negative advanced breast cancer.	OS
Other secondary	
To evaluate the safety and tolerability of LEE011 in combination with tamoxifen + goserelin or a NSAI + goserelin.	Frequency/ severity of adverse events, lab abnormalities
To evaluate the two treatment arms with respect to response rate and clinical benefit rate (CBR).	ORR as defined by RECIST 1.1. CBR, defined as percentage of patients with CR, PR per RECIST 1.1 or SD lasting 24 weeks or longer
To describe time to response (TTR) and duration of response (DOR) in each treatment arm.	Time to response and duration of response per RECIST 1.1
To evaluate the two treatment arms with respect to time to deterioration of ECOG PS.	Time to definitive deterioration of the ECOG PS from baseline

Objective	Endpoint
To evaluate patient reported outcomes for health-related quality of life in the two treatment arms.	Time to 10% deterioration in the global health status/QOL scale score of the EORTC QLQ-C30 Change from baseline in the global health status/QOL scale score of the EORTC QLQ-C30

2 Definitions and general methodology

2.1 Definitions

2.1.1 Study drug and study treatment

Study drug is defined as ribociclib or matching placebo.

Study treatment is defined as ribociclib + (tamoxifen or a NSAI) + goserelin, or matching placebo + (tamoxifen or a NSAI) + goserelin.

Cross-over open-label ribociclib treatment will refer to ribociclib drug administered to patients randomized to placebo plus tamoxifen/NSAI plus goserelin arm who subsequently cross-over to ribociclib plus NSAI plus goserelin (cross-over period).

Cross-over open-label ribociclib plus NSAI plus goserelin treatment will refer to the combination of drugs ribociclib plus NSAI plus goserelin administered during the cross-over period.

2.1.2 Date of first administration of study drug

The date of first administration of study drug is defined as the first date when a nonzero dose of study drug is administered and recorded on the dose administration DAR CRF. The date of first administration of study drug will also be referred to as start of study drug. Similar definitions apply for the other components of study treatment.

For analyses related to the cross-over period, date of first administration of cross-over open-label ribociclib treatment is defined as the first date when a non-zero dose of cross-over open-label ribociclib treatment is administered and recorded on the DAR CRF, after the date of cross-over recorded on the cross-over Details CRF.

2.1.3 Date of last administration of study drug

The date of last administration of study drug is defined as the last date when a nonzero dose of study drug is administered and recorded on the DAR CRF. Similar definitions apply for the other components of study treatment.

For analyses related to the cross-over period, date of last administration of cross-over open-label ribociclib treatment is defined as the last date when a non-zero dose of cross-over open-label ribociclib treatment is administered and recorded on the DAR CRF, after the date of crossover recorded on the cross-over Details CRF.

2.1.4 Date of first administration of study treatment

The date of first administration of study treatment is defined as the first date when a nonzero dose of any component of study treatment is administered and recorded on the DAR CRF. The date of first administration of study treatment will also be referred to as the start of study treatment.

For analyses related to the cross-over period, date of first administration of cross-over open-label ribociclib plus NSAI plus goserelin treatment is equal to the date of first administration of cross-over open-label ribociclib treatment.

2.1.5 Date of last administration of study treatment

The date of last administration of study treatment is defined as the last date when a nonzero dose of any component of study treatment was administered and recorded on the DAR CRF.

For analyses related to the cross-over period, date of last administration of cross-over open-label ribociclib plus NSAI plus goserelin treatment is defined as the last date when a non-zero

dose of any component of the cross-over open-label ribociclib plus NSAID plus goserelin treatment was administered and recorded on the DAR CRF during the cross-over period.

2.1.6 Study day

The study day will be calculated as:

- The date of the event (visit date, onset date of an event, assessment date etc.) – reference start date + 1 if event is on or after the reference start date.
- The date of the event (visit date, onset date of an event, assessment date etc.) – reference start date if event precedes the reference start date.

The reference start date for safety assessments (e.g., adverse event onset, laboratory abnormality occurrence, vital sign measurement, dose interruption etc.) is the start of study treatment. (Note: if an adverse event starts before the start of study treatment the study day displayed on the listing will be negative).

The study day will be displayed in data listings.

For analyses related to the cross-over period, study day is defined as above, with the reference date being the date of first administration of cross-over open-label ribociclib treatment.

2.1.7 Baseline

For safety evaluations (e.g., laboratory assessments and ECG), the last available assessment before or on the start date of study treatment will be used as the ‘baseline’ assessment. Assessments specified to be collected post-dose on the first date of treatment are not considered as baseline values.

If patients have no value as defined above, the baseline results will be considered missing.

For cross-over analyses, the last available assessment before or on the date of first dose of cross-over open-label ribociclib treatment will be used as the ‘baseline’ assessment.

2.1.8 On-treatment assessment/event

Safety summaries and selected summaries of deaths will summarize only on-treatment assessments/events.

Double-blind on-treatment period:

An on-treatment assessment/event is defined as any assessment/event in the following time interval:

[date of first administration of study treatment, the earliest between the date of last administration of study treatment + 30 days and the date of first administration of cross-over open-label ribociclib plus NSAID plus goserelin treatment – 1 day], i.e., including the lower and upper limits.

The double-blind on-treatment period is the **default** on-treatment period used in the analyses unless specified otherwise.

Cross-over on-treatment period:

An on-treatment assessment/event is defined as any assessment/event in the following time interval: [date of first administration of the cross-over open-label ribociclib plus NSAID plus goserelin treatment, date of last administration of the cross-over open-label ribociclib plus NSAID plus goserelin treatment + 30 days], i.e., including the lower and upper limits.

(Note: However, the calculation of study treatment duration will use different rules as specified in [Section 3.5.1](#)).

An AE started in the screening phase and ongoing in the on-treatment phase will not be considered as an on-treatment AE unless it has worsened.

If the last date of study treatment is missing, any assessment/event occurring after the start of study treatment will be considered as on-treatment.

Data listings will include all assessments/events, flagging those which are not on-treatment.

Note: The date of first administration of study treatment and the date of last administration of study treatment are defined in [Sections 2.1.4](#) and [2.1.5](#), respectively.

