## Amendment 6 (18-Jul-2019)

Study CLEE011E2301 was initiated in November 2014 and completed enrollment on 01-Aug-2016 with a total number of 672 randomized patients. The study met its primary endpoint of progression-free survival (PFS) at the time of the primary analysis in October 2017. The study met its key secondary endpoint of overall survival (OS) at the time of the planned second OS interim analysis in February 2019. Given these results, study participants will be unblinded in preparation for study closure. In addition, patients who are still receiving study treatment in the placebo arm, will be allowed to cross over to the ribociclib arm, based on the Investigator's judgement and an individualized benefit risk decision.

As of 03-July-2019, there are still 135 patients ongoing on study treatment, including 89 patients on ribociclib and 46 patients on placebo.

The purpose of this amendment is to:

- i. Unblind patients and investigators in order to allow for knowledge of patient's current treatment allocation
- ii. Allow for patients receiving placebo the opportunity to cross over to treatment with LEE011 per Investigator discretion
- iii. Provide guidance for patients receiving placebo + tamoxifen, who as per Investigator discretion will cross over to LEE011, to switch to an NSAID, if they are to cross over to treatment with LEE011. These patients will complete a wash out period of 5 half-lives.
- iv. Clarify end of study (EOS) and include information on post-study drug access
- v. Specify that central safety assessments can cease and all laboratory and ECG assessments should be performed locally and clarify the frequency of assessments
- vi. Specify that patient reported outcome (PRO) measures should no longer be collected  
[REDACTED]
- viii. Update the laboratory assessments to remove phosphorous and, per the IB, add serum pregnancy testing at EOT

Following this protocol amendment and the unblinding of study participants, the word "placebo" refers to the original treatment allocation in the study. Physical placebo capsules no longer need to be administered but the wording has been kept in places in the protocol to avoid confusion.

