At the time of protocol amendment 6, minimal follow up for all patients on study treatment is 36 months. Central laboratory hematology, biochemistry and ECG assessments will cease and all tests should be performed locally. Patients originally randomized to the LEE011 arm and continuing with open label LEE011 plus endocrine treatment and patients in the placebo arm that elect to continue with their current treatment (i.e. endocrine treatment alone), should have safety assessments and clinic visits as frequently as clinically indicated, but not less frequently than every 12 weeks. Tumor assessments will continue as clinically indicated as described in Section 7.2.1.1 (see Table 7-1a). Instructions for patients electing to cross-over from placebo to LEE011 at the next scheduled visit:

[figure not shown]
Patients currently receiving placebo plus NSAID plus goserelin and electing to cross-over to LEE011 plus NSAID plus goserelin, can commence LEE011 on Day 1 of their next planned cycle.

Of Note: Patients currently receiving placebo plus tamoxifen plus goserelin and elect to cross-over to the LEE011 arm, must first switch from tamoxifen to an NSAID. At least 5 tamoxifen half-lives (35 days) must elapse, before LEE011 is added. See [Section 6.1](#) for more details.

All patients commencing LEE011 after cross-over from placebo will need to have local hematology, electrolyte and liver function biochemistry tests every two weeks for the first 2 cross over cycles of LEE011 treatment, then at the beginning of cross over cycles 3 to 6, then as clinically indicated, but not less frequently than every 12 weeks. They need to have ECG for QT assessment on the first day before the administration of LEE011. LEE011 should be initiated only in patients with QTcF values <450 msec. The ECGs should be repeated on cross over Cycle 1 Day 15, on cross over Cycle 2 Day 1 and then as clinically indicated. The assessment schedule for patients who will cross-over is presented in [Table 7-1b](#). Consult [Table 6-3](#), [Table 6-4](#) and [Table 6-5](#) for monitoring frequency in cases of hematologic toxicity, liver function abnormalities or QT prolongation respectively.

**Table 7-1a Visit evaluation schedule – Patients that, after protocol amendment 6, continue with their originally randomized study treatment**

Visit name	Category	Reference to Protocol Section	Screening Phase		Treatment Phase							Post-treatment Phase			

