3.7.1.3 General rules for AE Reporting

AE summaries will include all AEs starting on or after study Day 1 (i.e., on or after the day of the first intake of study treatment) and starting no later than 30 days after the last administration of study treatment or the date of the day prior to the start of cross-over open-label ribociclib plus NSAID plus goserelin treatment (see [Section 2.1.5](#)). All AEs will be listed. AEs starting prior to study Day 1 and AEs starting later than 30 days after the last treatment date or the date of the day prior to the start of cross-over open-label ribociclib plus NSAID plus goserelin treatment will be flagged in the listings. AEs starting during the cross-over on-treatment period will be listed separately.

AEs will be summarized by presenting the number and percentage of patients having at least one AE, having at least one AE in each primary system organ class, and for each preferred term using MedDRA coding. A subject with multiple occurrences of an AE will be counted only once in the AE category.

Separate AE summaries will be presented by primary system organ class, preferred term, and maximum grade. A patient with multiple grades for an AE will be summarized under the maximum grade recorded for the event. AE with missing CTCAE grade will be included in the ‘All grades’ column of the summary tables.

In AE summaries the primary system organ class will be presented alphabetically and the preferred terms will be sorted within primary SOC in descending frequency. The sort order for the preferred term will be based on their frequency in the ribociclib arm.

The frequency of grade 3 and 4 AEs will be summarized separately.

Any information collected (e.g. grades, relationship to study treatment, action taken etc.) will be summarized and listed as appropriate.

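### The final SAP's 'double-blind' on-treatment period has no limit at the Amendment 6 unblinding, so by-arm safety tables carry open-label time under a blinded label

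*SAP*

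**What the plan says.** The SAP file holds two plans: one for the primary PFS report, based on protocol amendment 4, and one for the final report, based on amendment 7. This point concerns the second.

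Final SAP 2.1.8 starts the 'double-blind' on-treatment period at the first dose of study treatment. It ends at "the earliest between the date of last administration of study treatment + 30 days" and the day before the first dose of crossover treatment. This is the default "on-treatment period used in the analyses unless specified otherwise". Section 2.1.5 defines last administration as "the last date when a nonzero dose of any component of study treatment was administered", so endocrine therapy alone keeps the period open. Sections 3.7, 3.7.1.3 and 3.7.2 repeat the same limits; adverse events, for example, count when "starting no later than 30 days after the last administration of study treatment" or before crossover. Section 3.7.1.4 produces the adverse event tables by treatment group.

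On blinding, final SAP 1.1 states that "with protocol amendment 6, study participants were unblinded". Protocol 8.3 says that everyone is unblinded centrally. Protocol 7.1 describes patients in the ribociclib arm as "continuing with open label LEE011 plus endocrine treatment". The Amendment 6 text says "Physical placebo capsules no longer need to be administered". Section 1 of the final SAP nevertheless says that all its final-analysis decisions "have been made prior to database lock and unblinding of the study data".

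**The concern.** A table headed double-blind tells the reader that the patient and the investigator did not know the allocation when the events were reported, attributed and acted on. After Amendment 6 that is untrue for anyone still on treatment. The label matters most where judgement enters: events suspected to be related to treatment, and events leading to discontinuation, dose reduction or interruption. Ascertainment changed as well. Under Protocol 7.1, continuing patients moved to visits as clinically indicated, at least every 12 weeks, with local laboratory tests and ECGs.

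The statement in section 1 compounds this. It tells the reader that the final SAP was fixed before anyone could know allocation or results, which the rest of that SAP contradicts.

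**Working it through.** **1. The window.** Let L be the last nonzero dose of any component, X the first crossover ribociclib dose and U the date of unblinding. The SAP ends the period at min(L + 30 days, X − 1 day). U does not appear.

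- No crossover: the period ends at L + 30, so all time from U to L + 30 counts as double-blind.
- Crossover: the time from U to X − 1 counts as double-blind.
- Placebo plus tamoxifen, then crossover: Protocol 6.1, 6.3.1.1 and 7.1 require a 35-day tamoxifen washout on an NSAI plus goserelin before ribociclib. Final SAP 2.1.4 dates the start of crossover treatment from the first ribociclib dose. The washout is therefore inside the 'double-blind' period, although allocation is known and the endocrine partner has changed.

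**2. Counts stated in the protocol.** Amendment 6, 03-Jul-2019: 89 ribociclib + 46 placebo = 135, as stated. Amendment 7, 08-Jan-2020: 79 + 35 = 114, as stated. Eight of the 35 had crossed over, leaving 35 − 8 = 27.

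**3. Share of patients.** 135 / 672 = 20.1%. This is an upper bound on patients who went on being treated after unblinding. The count predates Amendment 6 (18-Jul-2019) and the ethics approval needed to implement it. In January 2020 the figure was 114 / 672 = 17.0%.

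**4. Balance between arms.** Headcount in July 2019: 89 / 46 = 1.93. In January 2020: 79 / 27 = 2.93. Keeping the eight crossed-over patients gives 79 / 35 = 2.26, but the SAP moves them to the crossover period. For person-time, assume straight-line decline over the 189 days (189 / 30.4375 = 6.21 months):

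- ribociclib: (89 + 79) / 2 × 6.21 = 522 patient-months
- placebo: (46 + 27) / 2 × 6.21 = 227 patient-months
- ratio: 2.3

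The first weeks of that interval were still blinded. The final data cut-off and individual unblinding dates are not given, so no later ratio can be computed without further assumptions.

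**5. How far a table could move.** Assume 336 patients per arm from the 1:1 allocation. Then 89 / 336 = 26.5% and 46 / 336 = 13.7%, a gap of 43 / 336 = 12.8 points. Let q be the share of these patients with a first or worsened event after unblinding, equal in both arms. The documents do not give q. The between-arm difference in crude incidence shifts by 12.8 × q points:

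| q | shift (points) |
|---|---|
| 5% | 0.6 |
| 10% | 1.3 |
| 20% | 2.6 |
| 30% | 3.8 |

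Because q is the same in both arms, this shift comes from unequal numbers still on treatment. It does not measure bias from unblinding.

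**6. The timing statement.** Final SAP section 1 rests on amendment 7. Amendment 7 reports eight patients who had already crossed over after the Amendment 6 unblinding. Final SAP 1.1 records that unblinding, and 1.2 says PFS and OS had already tested significant and been reported. Decisions in a plan built on amendment 7 cannot all predate unblinding. The same sentence stands in section 1 of the primary-analysis SAP, where it fits, so it was probably carried over.

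**The case against.** The strongest reply is that the window follows the protocol. Protocol 10.5.3.1 defines on-treatment as first dose to 30 days after last dose and asks only that crossover data be summarised separately. Amendment 6 revised that section without adding a cut at unblinding. This stands as a defence of the window's length. It does not defend its name.

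The consequence is also limited. Protocol 10.7.2 makes any analysis after amendment 7 descriptive, and the final SAP plans no between-arm test of adverse events. The primary-analysis SAP covers safety while patients and investigators were blinded. Crossover ribociclib data are properly kept apart. All of this stands.

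A reader might infer that open-label reporting drives the arms apart. The documents do not show this. Each patient counts once per category at maximum grade, and Protocol 7.1 puts minimum follow-up at 36 months for patients still on treatment, so only a late first or worsened event alters a table. Sparser visits could lower ascertainment. Laboratory grades use observed values only. Unequal exposure existed before unblinding too, and a cut would not remove it.

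A reader might also infer that the open-label data are 3:1 ribociclib throughout. That is a headcount on one date; it was 1.9:1 six months earlier.

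One practical objection also stands. The SAP names a case report form source for the crossover date but none for the date of unblinding.

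**Conclusion.** The point holds as a labelling and documentation error. By-arm tables called double-blind will contain open-label data from up to 20% of randomised patients, in a ratio that rose from 1.9:1 to 2.9:1 between the two dates the protocol reports. This follows directly from the text of 2.1.8 and needs no assumption. The per-arm percentages assume 336 patients in each arm, and the 0.6 to 3.8 point range rests on an assumed q.

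The documents do not support saying that the final safety comparison is biased in a known direction or by a known amount, or that any efficacy or primary-analysis safety conclusion is affected. Nor do they support replacing the full-period tables, which are informative once correctly named. The statement in section 1 is wrong as written, whatever is decided about the window.

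**What to change.** - Rename the period throughout the final SAP, for example 'randomized-treatment on-treatment period', and keep the full-period tables under that name.
- Add key adverse event tables cut at the day before unblinding: treatment-related events, and events leading to discontinuation, reduction or interruption. Use the patient's own unblinding date or, if it was not recorded, the date the site implemented Amendment 6.
- Show later events, including those in the tamoxifen washout, separately as open-label continuation by original arm.
- Correct section 1 to say that the final SAP was written after the PFS and OS results were known and patients had been unblinded.

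The cost is SAP wording, one derived date and a few extra tables. The availability of a per-patient unblinding date should be checked first. The cut does not address unequal exposure between arms, which would need exposure-adjusted rates.
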